Objective(s):	The primary objective is to assess the survival rate of dentures with SR Phonares II teeth after more than 10 years. The secondary objectives asses the quality of the dentures concerning aesthetic, functional and biological properties.
Outcome(s):	The primary outcome of the study is the survival rate of the dentures with the tested denture teeth. The secondary outcomes are all linked to the quality of the materials used (surface lustre, staining, plaque accumulation, color match, aesthetic anatomical form, fracture, marginal adaptation, occlusal contour, wear patients view, integrity of adjacent natural teeth, adjacent mucosa, oral health).
Design:	Retrospective evaluation

Inclusion / exclusion criteria:	Subjects fulfilling all inclusion criteria are eligible for the investigation: informed consent signed and understood by the subject, partial or full denture with SR Phonares II teeth, dentures delivered in the internal clinic between August 2010 and August 2012, to be able to visit the internal clinic (Exception: Patients with limited mobility are also included if another person can carry the dentures to the internal clinic of Ivoclar Vivadent AG for the examination.). The presence of any of the following exclusion criteria will lead to the exclusion of the subject: patient does not wear the dentures regularly, health status (physical and mental) does not allow participation.
Measurements and procedures:	The intraoral situation will be examined similar to a standard dental examination. The dentures are then removed, cleaned and examined extraoral. Pictures and an impression of the dentures are taken.
Intervention:	The examinations do not differ from standard dental examinations. Impressions of the back teeth of the dentures are taken extraoral and stone casts are poured. They are used for analysis of wear and microscopical analysis.
Control intervention (if applicable):	n.a.
Number of subjects with rationale:	22 patients that were supplied with dentures with SR Phonares II teeth (in total 43 dentures) in the internal clinic of Ivoclar Vivadent AG between August 2010 and August 2012.
Duration of the investigation:	6 months
Investigation schedule:	October 2022 First- subject –In (planned) March 2023 Last- subject –Out (planned)
Investigator(s):	[name] [name] Fürstentum Liechtenstein Tel.: [REDACTED] Mail: [REDACTED]

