Investigational Site(s):	This is a single centre study. R&D Clinic Ivoclar Vivadent AG [name] Fürstentum Liechtenstein
Statistical considerations:	Since the study is retrospective with a small cohort and no control group, mainly descriptive statistical analysis will be performed. The obtained data, especially the survival rate will be discussed and compared with data from the literature. A minimal sample size of 41 dentures was calculated with absolute error (precision of 10% and standard normal variate of 5% (type 1 error)).
Compliance statement:	This investigation will be conducted in compliance with the CIP, the current version of the Declaration of Helsinki, ISO14155, ICH-GCP (as far as applicable) as well as all national legal and regulatory requirements.

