4. INVESTIGATION SCHEDULE

Investigation Periods	Patient information	Consent (ICF)	Recall
Visit	0	1	1
Time (day)	-3	0	0
Patient Information by phone	x		
Patient consent (ICF)		x	
Primary Variables			x
Secondary Variables			x
Dental radiograph			(x)
Adverse events			x
Device Deficiencies			x

(x) dental radiographs of a single tooth or dental implant will only be taken if necessary for medical reasons independent of the clinical trial.

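### Secondary denture items are graded only on dentures present at the recall, so each result is conditional on survival and too favourable if lost dentures failed on that item more often than examined ones

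*Combined protocol and SAP*

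**What the plan says.** The primary outcome is a denture survival rate after more than 10 years of wear, so the plan allows for some dentures having failed before the visit. The secondary objective concerns the aesthetic, functional and biological quality of the dentures. In the Outcome(s) row of the synopsis, "The secondary outcomes are all linked to the quality of the materials used", and the list includes fracture, wear, staining, surface lustre and occlusal contour.

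The Measurements and procedures row explains how the denture is assessed: "The dentures are then removed, cleaned and examined extraoral". The Intervention row adds, as the basis for the wear analysis, "Impressions of the back teeth of the dentures are taken extraoral and stone casts are poured". In Section 4 (Investigation schedule), the row "Secondary Variables" is marked only under Recall, visit 1, day 0.

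The cohort is "22 patients that were supplied with dentures with SR Phonares II teeth (in total 43 dentures"). The statistical considerations describe a mainly descriptive analysis. The synopsis and schedule give no denominator for the secondary items, no rule for a denture that no longer exists at the recall, and no step that takes past failures or their causes from clinic records.

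**The concern.** An item such as fracture or wear can end a denture's service and is also a graded secondary outcome. If the denture was discarded or remade because it fractured, there is nothing to examine at the recall and it disappears from the fracture result. The missing grade is then related to the outcome being graded. This is truncation by failure, and counting the survival rate correctly does not cure it: the loss appears in the primary outcome but does not return to the item table.

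What is at stake is the reading of the secondary results. A low fracture or wear percentage could reflect good material, or it could reflect that the worst dentures were already gone. The plan also intends to compare its data with the literature, and grades conditional on survival are not comparable between series whose survival differs.

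**Working it through.** **The plan's own figure.** The synopsis states "A minimal sample size of 41 dentures was calculated", with "precision of 10% and standard normal variate of 5% (type 1 error"). The usual formula for estimating one proportion is n = z² p(1 − p) / d², with z = 1.96 and d = 0.10. No expected proportion p is stated. With p = 0.88, n = 1.96² × 0.88 × 0.12 / 0.10² = 40.57, which rounds up to 41. With p = 0.85 the result is 49, and with p = 0.90 it is 35. A survival of about 88% is therefore inferred from the figure 41. It is used below only to choose a plausible number of losses.

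**When the item result is too favourable.** Let N be the dentures of known status, L those lost before the recall, k the lost dentures that failed on the item, and f the examined dentures graded unacceptable on it.

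- Among examined dentures: f / (N − L).
- Over all dentures of known status: (f + k) / N.
- The first is smaller than the second exactly when k / L > f / (N − L).

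So the direction depends on whether lost dentures failed on the item more often than examined ones. If they failed less often, the examined-only figure is slightly unfavourable instead.

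**Illustration 1 (assumed inputs).** N = 41, L = 5 (36/41 = 88% survival), f = 2.

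| Losses that were fractures (k) | Among examined | Over all 41 |
|---|---|---|
| 0 | 2/36 = 5.6% | 2/41 = 4.9% |
| 1 | 2/36 = 5.6% | 3/41 = 7.3% |
| 5 | 2/36 = 5.6% | 7/41 = 17.1% |

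Here one fracture among the five losses is enough to reverse the direction (1/5 = 20% against 5.6%).

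**Illustration 2 (assumed inputs).** More losses widen the range. With L = 8 and f = 2, the examined-only figure is 2/33 = 6.1%, against 2/41 = 4.9% to 10/41 = 24.4% over all 41.

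**Illustration 3 (all 43 supplied dentures).** With L = 5 and no unacceptable grade among the 38 examined, the item reads 38/38 = 100% acceptable. Over all 43 it is 100% if no loss was due to the item, 42/43 = 97.7% if one was, and 38/43 = 88.4% if all five were.

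The documents supply only 41, 43, the 10% precision and the 5% error. The values of L, k and f are assumptions.

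**The case against.** The strongest reply is that the quality of dentures still in service after more than 10 years is a legitimate descriptive target. The objective does not say that quality must be judged over every denture supplied. Losses are reported in the survival rate, and device deficiencies are recorded at the recall, so heavy loss through fracture would not be hidden from a reader who takes both results together. These are also descriptive secondary outcomes in an uncontrolled cohort of 22 patients. This stands in part: the examined-only figures are worth reporting, provided that they are labelled for what they are.

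Further limits also stand. A failed denture that was kept and brought to the visit can still be graded. Losses for unrelated reasons need not bias an item. The text available ends at Section 4, so a handling rule in a later section cannot be excluded.

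A reader might go further and propose basing the quality statement on one composite: in service and acceptably graded, with every failure counted as unacceptable on every item. That is not a clear improvement. It caps each item at the survival rate. With 36 of 41 in service, colour match could not exceed 88% even if no denture had ever shown a mismatch. It can serve as a bound beside the other figure, but not as the sole basis.

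The objection does not remove the main point: the primary survival rate does not say how many losses belong to which item.

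**Conclusion.** The point holds in conditional form. Under the procedures described, denture-level items are graded once, on dentures physically present at the recall, and nothing in the synopsis or schedule brings an earlier loss into the item it failed on. Each result is conditional on survival, and is too favourable when lost dentures failed on the item more often than examined ones did.

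The size cannot be derived. Under the assumptions of the first illustration, 5.6% among those examined corresponds to anything from 4.9% to 17.1% over all 41.

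Two stronger readings are tempting and not supported. One is that quality is certainly overstated: that needs the causes of loss, which the documents do not give. The other is that the real fracture rate is 17.1%, or, with eight losses, four times the observed one (24.4% against 6.1%): those figures come from assuming that every loss was a fracture. Nor does the plan state that survivors are the denominator; this follows from how and when the grades are collected, in the absence of another rule.

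The matter should be corrected in the plan. It concerns the secondary outcomes and does not affect the primary survival rate.

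**What to change.** For each denture-level item, report two figures.

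1. The grade distribution, labelled *among dentures in service at recall*, with the number examined.
2. Beside it, the result over all dentures of known status out of the 43 supplied. Count a failed denture as unacceptable on the item that caused its loss where the cause is known. Where the cause is not known, show the range from no such denture unacceptable to every such denture unacceptable.

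Word the conclusion on quality as conditional on survival and read it together with the survival rate. Do not rest it on the any-cause composite alone. Patient-level items (mucosa, adjacent natural teeth, oral health) are outside this change.

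The cost is a short addition to the plan, one extra column per item, and a note of the cause of each loss where it can be recovered. The downside is that the quality figures become wider or somewhat less favourable. Where causes cannot be recovered after 10 years, the range may be too wide to say much, but it will show how far the examined-only figure can be relied on.

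### The 10-point precision behind 41 dentures fits a symmetric normal-approximation formula at an unstated survival of about 88%; there, a Wilson or exact interval reaches 13 to 14 points below the estimate, more if dentures cluster within patients.

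*Combined protocol and SAP*

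**What the plan says.** All of this is in the synopsis (section 1).

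- Outcome(s): "The primary outcome of the study is the survival rate of the dentures with the tested denture teeth". The objective is to "assess the survival rate of dentures with SR Phonares II teeth after more than 10 years".
- Statistical considerations: "A minimal sample size of 41 dentures was calculated with absolute error", followed by "precision of 10% and standard normal variate of 5" per cent, the latter labelled as the type 1 error. It adds that "mainly descriptive statistical analysis will be performed", and that the survival rate will be set against published data.
- Number of subjects: "22 patients that were supplied with dentures with SR Phonares II teeth (in total 43 dentures"), so the available cohort is only two dentures above the stated minimum.

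The available text gives no expected survival rate, formula, sidedness or confidence-interval method. It does not say whether 10% means a symmetric half-width or a limit on the lower side.

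**The concern.** The 10% figure is the plan's only quantitative statement about its primary outcome. An absolute error combined with a standard normal variate points to the textbook formula for estimating one proportion, which rests on a symmetric interval. Near 88% survival only about 5 of 41 dentures would be expected to fail. With so few failures the sampling distribution is skewed, and a symmetric interval sits too high.

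The lower limit is the one that counts here. The sponsor makes the product, there is no control group, and the result will be read against the literature. A reader who takes the plan to mean plus or minus 10 points would think poor survival better excluded than the data can show. Most patients also contribute two dentures, and the formula makes no allowance for that.

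**Working it through.** **Inputs.** From the synopsis: n = 41, d = 0.10, type 1 error 5%, 43 dentures, 22 patients. Not in the documents and therefore assumed: the survival p, the sidedness, the interval method and the intraclass correlation (ICC).

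**1. Reproducing 41.** The formula is n = z² p(1−p)/d².

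- Two-sided, p = 0.88: 1.96² × 0.88 × 0.12 / 0.01 = 40.6, rounded up to 41. Neighbouring values miss: 0.87 gives 44, 0.89 gives 38, 0.50 gives 97. Solving backwards, p(1−p) = 41 × 0.01 / 1.96² = 0.1067, so p = 0.8785.
- One-sided (z = 1.645): p(1−p) = 41 × 0.01 / 1.645² = 0.1515, so p is about 0.81.

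The number 41 can therefore be matched, but not derived from what the plan states.

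**2. Intervals at 36/41 = 87.8%, 95% two-sided, dentures treated as independent.**

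| Method | Interval | Points below | Points above |
|---|---|---|---|
| Normal approximation (Wald) | 77.8% to 97.8% | 10.0 | 10.0 |
| Wilson | 74.5% to 94.7% | 13.3 | 6.9 |
| Clopper-Pearson | 73.8% to 95.9% | 14.0 | 8.1 |

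The Wald half-width is 1.96 × √(0.878 × 0.122 / 41) = 0.100, which is the plan's 10%. Total widths are 20.0 (Wald), 20.2 (Wilson) and 22.1 (Clopper-Pearson) points. Jeffreys gives 12.5 points below.

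**3. Other results.** At 39/41 the lower arm is 11.3 (Wilson) to 11.7 (Clopper-Pearson). With all 43 dentures, at 38/43, it is 12.9 to 13.5. On the one-sided reading, at 33/41, it is 11.9 to 12.9. At 41/41 the Wald interval has zero width, while the Wilson and exact lower limits are both 91.4%.

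**4. Coverage of the nominal 95% Wald interval, n = 41.** Sum the binomial probabilities of every count whose interval contains the true p.

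| True survival | 0.86 | 0.87 | 0.88 | 0.89 | 0.90 | 0.95 |
|---|---|---|---|---|---|---|
| Coverage | 93.1% | 90.2% | 87.7% | 93.7% | 92.0% | 87.4% |

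These six values lie between 87% and 94%, but coverage is a sawtooth and dips lower between them. At p = 0.92 the intervals for 40/41 and 41/41 both miss: 0.92⁴¹ + 41 × 0.92⁴⁰ × 0.08 = 0.033 + 0.117 = 0.150, so coverage cannot exceed about 85%. The error is mainly in one direction. At p = 0.88 the intervals for 39, 40 and 41 survivors lie wholly above the truth, with total probability 11.6% against a nominal 2.5%. Wilson coverage is 94.4% at 0.88 and 94.7% at 0.95.

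**5. Dentures within patients.** Average cluster size is 43/22 = 1.95. The design effect is 1 + (1.95 − 1) × ICC, and the effective size is 41 divided by it. Wilson at 87.8%:

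| Assumed ICC | Design effect | Effective n | Wilson interval |
|---|---|---|---|
| 0 | 1.00 | 41 | 74.5% to 94.7% |
| 0.1 | 1.10 | 37.4 | about 74% to 95% |
| 0.5 | 1.48 | 27.8 | about 71% to 96% |

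**The case against.** The plan commits to no Wald interval. It promises mainly descriptive analysis, and choosing n with a normal-based formula does not oblige anyone to report a normal-based interval. The available text ends with the investigation schedule in section 4, so a fuller statistical section may exist that was not seen. This stands: the zero width at 41/41 and the poor coverage describe what would follow if the sizing formula were carried into the analysis, not an analysis the plan has announced.

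The 88% is back-solved and depends on a two-sided reading. This also stands, and the conclusion is conditional for that reason. The one-sided reading still gives a lower arm above 10 points.

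A reader might infer that the normal approximation breaks down at this sample size, or that 13 to 14 points is the one true error. The documents support neither. Wilson's average half-width at 36/41 is 10.1 points, so 10% read as an average half-width is nearly kept. The lower arm varies with method and result: Jeffreys is already just under 10 at 39/41, and with 42/43 surviving Wilson and Clopper-Pearson fall to 9.7 and 10.0. The coverage at 0.88 is near a local low point.

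Finally, the cohort is fixed and the available text ties no threshold or test to the lower limit, so nothing in the conduct of the study would change. That limits the weight of the point. It does not remove the case for stating the precision correctly.

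**Conclusion.** The concern holds in conditional form. The plan's 10% matches the symmetric formula at about 88% survival, two-sided. If that was the assumption, Wilson and exact intervals at 36/41 run from about 74% to 95–96%. The symmetric lower limit of 77.8% is then 3 to 4 points too favourable. For Wilson the change is almost entirely a downward shift; Clopper-Pearson is also about 2 points wider in total.

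These figures treat dentures as independent. Under an assumed ICC of 0.5 the Wilson lower limit falls to about 71%, some 17 points below the estimate (87.8 − 70.9). The ICC values are illustrations; the documents give none.

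More dentures are not available as a remedy. A 10-point lower arm near 88% would need roughly 67 (Wilson) to 70 (Clopper-Pearson) independent dentures, and 43 exist. What can be corrected is the statement of precision and the choice of interval.

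**What to change.** In the statistical considerations:

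1. State the survival rate assumed for the sample size, its source, and whether the 5% is one- or two-sided.
2. Say that the survival proportion will be reported with a Wilson or Clopper-Pearson 95% interval, using an effective sample size or another method that allows for dentures within patients.
3. Restate the precision on that basis as a range over assumed ICCs. For example, if 36 of 41 survive, the Wilson 95% interval is about 74% to 95% for an ICC of 0 to 0.1, widening to about 71% to 96% for an ICC of 0.5. Quoting 74% to 95% alone would again assume near-independence.

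The cost is a few sentences and a modest change to the analysis code. No further patients or measurements are needed. The drawback is that the stated precision becomes less favourable than plus or minus 10 points.

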2. ABBREVIATIONS

AE	Adverse Event
ADE	Adverse Device Effect
ASADE	Anticipated Serious Adverse Device Effect
ASR	Annual Safety Report
CA	Competent Authority (e.g. Swissmedic)
CEC	Competent Ethics Committee
CIP	Clinical investigation plan
ClinO	Ordinance on Clinical Trials in Human Research (in German KlinV, in French Oclin, in Italian OSRUM)
ClinO-MD	Ordinance on Clinical Trials with Medical Devices (in German: KlinV-Mep, in French: Oclin-Dim, in Italian: OSRUM-Dmed)
CRF	Case Report Form (pCRF paper CRF; eCRF electronic CRF)
DD	Device Deficiency
DMC / DSMC	Data Monitoring Committee, Data Safety Monitoring Committee
Ho	Null hypothesis
H1	Alternative hypothesis
HRA	Federal Act on Research involving Human Beings (in German: HFG, in French: LRH, in Italian: LRUM)
IB	Investigator's Brochure
ICF	Informed Consent Form
ICH-GCP	International Council for Harmonisation – guidelines of Good Clinical Practice
IFU	Instruction For Use
ISF	Investigator Site File
ISO	International Organisation for Standardisation
ITT	Intention to treat
MedDO	Medical Devices Ordinance (in German: MepV, in French: Odim, in Italian: Odmed)
MD	Medical Device
MDR	Medical Device Regulation (EU) 2017/745 of 5 April 2017
PI	Principal Investigator
SADE	Serious Adverse Device Effect
SAE	Serious Adverse Event
SDV	Source Data Verification
SNCTP	Swiss National Clinical Trials Portal
SOP	Standard Operating Procedure
USADE	Unanticipated Serious Adverse Device Effect

3. SUMMARY OF THE REVISION HISTORY IN CASE OF AMENDMENTS

Version Nr, Version Date	Chapter	Description of change	Reason for the change

4. INVESTIGATION SCHEDULE

Investigation Periods	Patient information	Consent (ICF)	Recall
Visit	0	1	1
Time (day)	-3	0	0
Patient Information by phone	x		
Patient consent (ICF)		x	
Primary Variables			x
Secondary Variables			x
Dental radiograph			(x)
Adverse events			x
Device Deficiencies			x

(x) dental radiographs of a single tooth or dental implant will only be taken if necessary for medical reasons independent of the clinical trial.

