1. SYNOPSIS

Sponsor / Sponsor-Investigator	Ivoclar Vivadent AG
Title:	Retrospective clinical evaluation of nano-hybrid-composite denture teeth SR Phonares II
Short title / Investigation ID:	Retrospective clinical evaluation of SR Phonares II Investigation ID: LL 5267725
Clinical Investigation Plan, version and date:	Version 2.0, 19.09.2022
Registration:	Registry at ClinicalTrials.gov of the U.S. National Library of Medicine (http://www.clinicaltrials.gov): The trial additionally registers in the supplementary federal database (Portal for clinical trials in Switzerland - SNCTP, https://www.kofam.ch/en/snctp-portal/) with its submission on BASEC. Furthermore, as soon as the new electronic system EUDAMED2 is operational, the clinical investigation will be retrospectively registered, if required.
Category and its rationale:	Category A1 The medical device has conformity marking and will be used according to its instruction for use. The subjects are not subjected to any additional invasive or stressful procedures compared with those applied under normal conditions of use of the product.

Name of the MD, Unique Device Identification (UDI), name of the manufacturer	SR Phonares II Article UDI SR Phonares II Ant. 6er OS71 A2 DIVO6448651 SR Phonares II Ant. 6er OS71 A3 DIVO6448661 SR Phonares II Ant. 6er OS72 A3 DIVO6448861 SR Phonares II Ant. 6er OB71 A3 DIVO6450461 SR Phonares II Ant. 6er OB72 A3 DIVO6450661 SR Phonares II Ant. 6er OB73 A3 DIVO6450861 SR Phonares II Ant. 6er OB73 A3.5 DIVO6450871 SR Phonares II Ant. 6er UL50 A2 DIVO6451651 SR Phonares II Ant. 6er UL51 A3 DIVO6451861 SR Phonares II Ant. 6er UL51 A3.5 DIVO6451871 SR Phonares II Ant. 6er UL52 A3 DIVO6452061 SR Phonares II Ant. 6er UL53 A3 DIVO6452261 SR Phonares II Typ 8er ONU3 A3 DIVO6453661 SR Phonares II Typ 8er ONU5 A3 DIVO6453861 SR Phonares II Typ 8er ONU5 A3.5 DIVO6453871 SR Phonares II Typ 8er ONU6 A3 DIVO6454061 SR Phonares II Typ 8er UNL3 A2 DIVO6454251 SR Phonares II Typ 8er UNL5 A3 DIVO6454461 SR Phonares II Typ 8er UNL5 A3.5 DIVO6454471 Ivoclar Vivadent AG [name]
Stage of development:	Post-market stage with CE marking
Background and rationale:	This retrospective study investigates the longevity of dentures with SR Phonares II teeth after a wearing period of more than 10 years.

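### No source is named for fractures, repairs or remakes between delivery and recall, and survival failure is not defined, so survival may be overstated

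*Combined protocol and SAP*

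**What the plan says.** - **Aim.** In the Synopsis (section 1), the background entry states: "This retrospective study investigates the longevity of dentures with SR Phonares II teeth after a wearing period of more than 10 years". The primary objective is "to assess the survival rate of dentures with SR Phonares II teeth after more than 10 years", and the design entry reads "Retrospective evaluation".
- **Outcomes.** "The primary outcome of the study is the survival rate of the dentures with the tested denture teeth". Fracture is not part of that definition. It is in the list introduced by "The secondary outcomes are all linked to the quality of the materials used". The Synopsis does not say what ends a denture's survival.
- **Cohort.** Eligibility requires "dentures delivered in the internal clinic between August 2010 and August 2012". The subject-number entry gives 22 patients and 43 dentures, all supplied by that same clinic.
- **Procedures.** The Synopsis describes an oral examination, inspection of the cleaned denture outside the mouth, pictures and an impression, with stone casts for wear and microscopy. A patient who cannot travel may have someone else bring the denture.
- **Timing.** In section 4, the rows "Primary Variables" and "Device Deficiencies" each carry one mark, under Recall (visit 1, day 0). No column or footnote refers to clinic files, repair history or the period since delivery.

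**The concern.** Survival over a decade depends on the history of each denture. The procedures described record its present condition. Two kinds of past event can escape them:

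- A tooth that fractured and was replaced years ago can look intact at recall.
- A denture that was remade or abandoned is not there to inspect. Its wearer may also fall outside eligibility, which requires a denture with the study teeth and excludes people who do not wear theirs regularly.

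Any missed event that counts as a failure moves survival in one direction only, in favour of the sponsor's product. Fracture and device-deficiency counts are exposed in the same way, however survival is defined. The Synopsis intends to set the survival rate beside published data. A reader of that comparison needs to know what was counted as a failure and over what period events were sought.

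**Working it through.** The point rests mainly on the text. The plan's one calculated figure, the minimum of 41 dentures, is a precision calculation and does not bear on how events are found, so there is no plan figure to reproduce here.

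**Step 1: period to be covered.** Delivery dates and the planned recall window come from the Synopsis.
- Shortest: 31 August 2012 to 1 October 2022 = 10.1 years.
- Longest: 1 August 2010 to 31 March 2023 = 12.7 years.

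**Step 2: what each described source can show.**

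| Event since delivery | Examination, pictures, impression at recall | Clinic files | Patient history |
|---|---|---|---|
| Denture still in service | Yes | Not needed | Not needed |
| Tooth fractured, then replaced or repaired | Not reliably | If done at this clinic | If remembered |
| Denture remade or no longer worn | Not from the old denture | If done at this clinic | If asked |
| Date and cause of any event | No | If recorded | Approximate |

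The available text describes the first source only.

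**Step 3: effect of one missed event.** Let *s* be failures seen and *m* failures missed among 43 dentures. If missed failures are counted as survivors:

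- reported survival = (43 − *s*)/43
- actual survival = (43 − *s* − *m*)/43
- overstatement = *m*/43

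The documents give no value for *m*. As an illustration, assume *s* = 2:

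| *m* (assumed) | Reported | Actual | Overstatement |
|---|---|---|---|
| 0 | 95.3% | 95.3% | 0 |
| 1 | 95.3% | 93.0% | 2.3 points |
| 2 | 95.3% | 90.7% | 4.7 points |
| 4 | 95.3% | 86.0% | 9.3 points |

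**Step 4: if the missing denture also leaves the denominator.** Reported survival becomes (43 − *s* − *m*)/(43 − *m*). With *s* = 2 and *m* = 2 this is 39/41 = 95.1%, against 39/43 = 90.7% actual, an overstatement of 4.4 points. The figure of 2.3 points per event is therefore exact only when all 43 dentures stay in the denominator.

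**Step 5: dependence on the definition.** If a repaired denture still in use counts as surviving, missed repairs leave survival unchanged. They would still be missing from the fracture or device-deficiency counts.

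**The case against.** The strongest reply is that the schedule says when items are recorded, not how far back they reach. In a one-visit study there is no other visit to mark, and a mark at recall is compatible with reading the file or taking a history that day. Status at recall is also cumulative: if survival means still in service, a denture in use after 10 years has survived the whole interval. Fracture is a secondary outcome, so a repair need not be a failure. The cohort is a known list, so an absent denture could be noticed. Only sections 1 to 4 are available, and a later section may define failure or describe a record review.

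All of this stands as a limit on the claim. What remains is that neither the procedures nor the schedule names such a look-back, and history-taking cannot be assumed when someone else brings the denture.

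A reader might be tempted by three stronger readings, which the documents do not support:

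- *Survival is overstated.* Nothing shows that any event was missed, and zero is possible.
- *The bias exceeds the stated 10% precision.* Five missed failures would give 5/43 = 11.6 points, but nothing in the documents supports five or any other number.
- *Adverse events should also be traced back to delivery.* The schedule marks them at recall, and the available text does not say that their reporting was meant to reach back before consent.

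**Conclusion.** The concern holds as a gap in data source and definition. For a study of survival beyond 10 years, the available plan describes only present-state examination, names no source for events between delivery and recall, and does not say which events end survival. Survival may be overstated, and fracture and device-deficiency counts understated.

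The size cannot be derived. It is zero if nothing is missed. For survival it is also zero if the missed events are not failures. Otherwise it is 2.3 points per missed failure, assuming all 43 dentures stay in the denominator. The conclusion rests on sections 1 to 4 alone. If a later section already defines failure and requires a record review, what remains is to show that source in the schedule.

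**What to change.** 1. Add a source to the section 4 schedule, *clinic records, delivery to recall*, marked for primary variables, fracture and device deficiencies.
2. For all 43 delivered dentures, abstract from the internal clinic's files the delivery date and the date and cause of every fracture, debonding, tooth replacement, repair and remake.
3. Ask each patient about work done elsewhere, by phone where another person brings the denture.
4. State before analysis which events count as survival failure (for example, remake or permanent loss from service). Report repaired dentures still in service separately.
5. Account for every one of the 43 dentures, including those remade, no longer worn or not examined, with the reason.
6. Show recall-day findings separately from events found in the records.

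**Cost.** Chart abstraction for 22 patients at the clinic that delivered the dentures, plus a few lines of text. This assumes the files exist. Capture of repairs done elsewhere will be incomplete because it depends on memory, and the reported survival may be lower.
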